7.3 Exclusion Criteria

A patient who meets any of the following exclusion criteria will not be eligible for inclusion

Protocol Version 4, 06 OCT 2021

Confidential

Page 29 of 70

in the study:

- 1. Recorded number of falls in previous 12 months and during trial. Participants who report multiple falls with potential loss of consciousness will be excluded
- 2. History of QTc-induced prolongation and willingness to limit use of over-the- counter, or prescription medicines (e.g. anti-histamines) known to prolong QTc interval. Corrected QT interval using Bazett's formula (QTcB) interval > 450 msec for males, or 470 msec for females, as detected by ECG and confirmed by physician. Participants who have a history of QTc-induced prolongation and are unwilling to limit use of medication will be excluded.
- 3. Evidence of abnormal cardiac function as defined by any of the following:
 - a. Myocardial infarction within 6 months of Cycle 1, Day 1
 - b. Symptomatic congestive heart failure (New York Heart Association > Class II)
 - c. Unstable angina
 - d. Unstable atrial fibrillation including paroxysmal atrial fibrillation. Medicated, stable atrial fibrillation will be assessed by the study doctor on a case-by-case basis
 - e. Frequent multifocal ventricular arrhythmia
- 4. Unable to swallow oral medications.
- 5. Gastrointestinal conditions that, in the opinion of the Investigator, could affect the absorption of study drug.
- 6. Use of any prescription or non-prescription (including herbal) medications, or consumption of foods known to be strong QT prolongation within 7 days prior to the first administration of LeracolTM and for the duration of the study. These include (but are not limited to):
 - a. Medications: See APPENDIX 7.
 - b. With significant central anticholinergic effects,
 - c. Sedatives,
 - d. Antiparkinsonian medications that cannot be stopped prior to study entry,
 - e. Any investigational treatment for AD
 - f. *Foods:* Grapefruit or Seville orange (or grapefruit- or Seville orange-containing products, including juices).
- 7. Current diagnosis of cancer (within 5 years) and/or undergoing chemotherapy,
- 8. Significant head injury within 5 years
- 9. Electrolyte imbalance (e.g. on high steroids, pituitary tumours, and Addison disease)
- 10. Hypokalaemia, hypomagnesaemia and hypocalcaemia
- 11. They have other neurologic or psychiatric diagnosis that in the opinion of the investigator could interfere with cognitive function,
- 12. Major surgery is planned during the conduct of the trial, or a clinical event has occurred in the six months preceding study inclusion that may compromise ability to participate for the duration of the study,
- 13. Evidence of stroke,

Protocol Version 4, 06 OCT 2021

Confidential

Page 30 of 70

Curtin University Study Protocol
Protocol No.: PIA-2020

- 14. Current diagnosis with a psychiatric disorder, or taking psychotropic medications,
- 15. Willing and able to undergo Magnetic Resonance Imaging (MRI)
- 16. Other excluded medications will be those that are;
 - Specifically contraindicated with Probucol, based on historic clinical indications for the treatment of cardiovascular disease. Stable use (for at least 3 months) of cholinesterase inhibitors and memantine will be allowed.
 - Patients on high dose loop-diuretics or thiazide diuretic medications, will be excluded if taking maximum dose of furosemide or Bendroflumethiazide
- 17. Self-reported active human immunodeficiency virus (HIV-1 or HIV-2), hepatitis B or hepatitis C virus (HCV) at the Screening visit.
- 18. Any inflammatory or chronic pain condition that necessitates regular use of opiates/opioids,.
- 19. Major surgery within 28 days of Day 1 Week 0, or minor surgical procedures within 7 days of Day 1 Week 0.
- 20. For women of childbearing potential, a pregnancy hCG test > 5 U/L at screening, or on Day 1, prior to dose administration.
- 21. Pregnant or breast-feeding (or planning to breastfeed) while on study through 15 days after the last dose of study drug.
- 22. Hypersensitivity or other clinically significant reaction to the study drug or its inactive ingredients.
- 23. Known substance abuse or medical, psychological, or social conditions that, in the opinion of the Investigator, may interfere with the patient's participation in the clinical study or evaluation of the clinical study results.

Any other condition or prior therapy that in the opinion of the Investigator would make the patient unsuitable for this study, including inability to cooperate fully with the requirements of the study protocol or likelihood of noncompliance with any study requirements

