- 8. Adequate coagulation laboratory assessments (i.e. results within normal ranges, per local laboratory definition) at screening.
- Lipids (total cholesterol, HDL and LDL) must be within < 1.5 x the upper limit of normal for the local laboratory reference range at the screening visit
- 10. FBC must be within < 1.5 x the upper limit of normal for the local laboratory reference range at the screening visit
- 11. Female volunteers:
 - a. Must be of non-childbearing potential (i.e., surgically sterilised [hysterectomy, bilateral salpingectomy, bilateral oophorectomy at least 6 weeks before the screening visit]) or postmenopausal (where postmenopausal is defined as no menses for 12 months without an alternative medical cause at the screening visit), or

Protocol Version 4, 06 OCT 2021

Confidential

Page 6 of 70

b. If of childbearing potential, must agree not to donate ova, not to attempt to become pregnant and, if engaging in sexual intercourse with a male partner, must agree to the use of acceptable forms of highly effective contraception (refer to Appendix 5) from the time of signing the consent form until at least 30 days after the last dose of the study drug.

12. Male volunteers:

- a. Engaging in any sexual intercourse, including those who are infertile and do not produce sperm (e.g. post-vasectomy), must abstain from unprotected sex until the End of Study visit or equivalent i.e. 4 days after last dose
- b. Must agree to abstain from sperm donation, and if engaging in sexual intercourse with a female of child bearing potential must agree to the use of an acceptable form of highly effective contraception (refer to Appendix 5) from the time of signing the consent form until at least 90 days after the last dose of study drug.
- 13. Have suitable venous access for blood sampling.
- 14. Be willing and able to comply with all study assessments and adhere to the protocol schedule and restrictions.
- 15. A study partner (partner/spouse/carer) consents to the minimum requirements:
 - a. will attend at least one screening visit
 - b. will be available via phone or in person to provide information to the study as required

Exclusion Criteria

A patient who meets any of the following exclusion criteria will not be eligible for inclusion in the study:

- Recorded number of falls in previous 12 months and during trial. Participants who report multiple falls with potential loss of consciousness will be excluded

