5 STUDY OBJECTIVES AND ENDPOINTS

The study objectives and endpoints are provided in Table 2, below.

Table 1. Study Objectives and Endpoints for Study PIA-2020

Objective(s)	Endpoint(s)
Primary	
• To evaluate the preliminary efficacy of 250 mg BID Lorelco TM on cognitive performance in Alzheimer's patients over a 102 week treatment period	Cognitive performance parameters include (but are not limited to): • Cognitive Subscale test (ADAS-Cog)
Secondary	
To evaluate:	 PET Scan visual assessment of amyloid load quantitative assessment of amyloid burden MRI Scan volumetric changes in the brain cerebral amyloid abundance Quality of life parameters to be assessed include (but are not limited to): Alzheimer's Disease Co-operative Study Mild Cognitive Impairment Activities of Daily Living scale (ADCS-MCI-ADL24) Depression Anxiety Stress Scale (DASS-21)
To assess the safety and tolerability of Lorelco™ in patients with Alzheimer's Disease	Safety and tolerability endpoints include: Incidence, type and severity of AEs Dose-limiting toxicities (DLTs) Changes from baseline in: electrocardiogram (ECG) parameters vital sign measurements body weight physical examination finding clinical laboratory parameters

Curtin University Study Protocol
Protocol No.: PIA-2020

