Patients will also undertake safety and other assessments as required on Days 1 (± 2 days) on Weeks 1, 2, 3, 4, 5, 15, 26, 39, 52, 65, 78 and 104.

A study design overview is shown in Figure 1.
Protocol Version 4, 06 OCT 2021 Confidential

Page 22 of 70

Curtin University Study Protocol
Protocol No.: PIA-2020

Figure 1. Study Design Overview

Patients will be screened between Day -56 to Day -1.

Safety and tolerability assessments will include vital signs, 12-lead ECGs, physical examinations, clinical laboratory tests (haematology, serum chemistry, coagulation, lipid analysis and urinalysis), and AE monitoring, as described in Section 11.8. Blood samples will be collected at specified times, as described in the schedule of assessments (APPENDIX 1).

Efficacy assessments include imaging using, PET scan and Magnetic Resonance Imaging (MRI) as described in Section 11.9. Imaging assessments will be performed at screening, and the 104 week visit or at last study visit if subject discontinues.

A final end of study visit will occur 4 weeks (\pm 2 weeks) following the last study drug administration.

There are no scheduled overnight confinement periods, however if patients experience any clinically significant adverse events (AEs) during the study, they may be admitted to the clinical facility for further observation at the discretion of the PI.

In the event of strong clinical benefit, and at the discretion of the study doctor, a participant may be reinstated in the study 4 weeks after discontinuation of the participant due to AE. This will be evaluated on a case by case basis.

Regardless of perceived benefit, participants cannot continue probucol at the end of the study as LorelcoTM is not approved for use in Australia. If strong clinical support is identified in the study, this will support effectiveness and phase III trials.

LorelcoTM will be evaluated at a single dose levels with dose increasing to BID by week 4 (Table 2). Thirty patients will initially be enrolled into single-patient cohorts and will be observed during the evaluation period (Week 2 Day 1 to Week 6).

If the patients do not experience any ≥Grade 2 AEs that are deemed related to study treatment, then additional patients may be dosed. The decision to commence dosing in additional patients will be at the discretion of the SRC following review of all AEs, clinical findings, laboratory results.

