7 PATIENT SELECTION

7.1 Number of Patients

Estimated sample sizes are calculated for the two primary outcome measurements: ADAS-Cog and GM atrophy (hippocampal). In order to ensure that the study has sufficient power to detect differences in both of the primary outcomes, the sample size chosen is the maximum of that calculated for each primary outcome.

The primary analysis was an intention-to-treat analysis and included all randomized participants. Data will be analysed using both Generalised Estimating Equations (GEE) and Bayesian Analysis.

The analysis of primary endpoints will use linear mixed-effects models, with random slopes and intercepts. For the ADAS-Cog, using mixed model analysis published estimates from the ADNI cohort17 suggest a sample size of 125 AD participants per trial arm (total N = 250) will be required for power at 0.8 to detect a drug effect of 25% over two years and assuming a decline from baseline of 1.10 standardised units on the composite (SD change = 0.83).

For the MRI markers, Ledig et al. $(2018)^{24}$ reported the sample sizes required for a 25% intervention reduction over two years based on 322 patients with AD (with 117 followed for 24 months) and a reduction of 10.2% (6.2) for hippocampus 18. Sample size calculations based on hippocampal volume suggest that 93 subjects per treatment arm are required (total N = 186).

Assuming a 20% attrition rate, a sample of 314 subjects will be recruited for the Cognitive study, and 233 subjects will be randomly chosen for the Imaging study.

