- b. If of childbearing potential, must agree not to donate ova, not to attempt to become pregnant and, if engaging in sexual intercourse with a male partner, must agree to the use of acceptable forms of highly effective contraception (refer to Appendix 5) from the time of signing the consent form until at least 30 days after the last dose of the study drug.

12. Male volunteers:

- a. Engaging in any sexual intercourse, including those who are infertile and do not produce sperm (e.g. post-vasectomy), must abstain from unprotected sex until the End of Study visit or equivalent i.e. 4 days after last dose
- b. Must agree to abstain from sperm donation, and if engaging in sexual intercourse with a female of child bearing potential must agree to the use of an acceptable form of highly effective contraception (refer to Appendix 5) from the time of signing the consent form until at least 90 days after the last dose of study drug.
- 13. Estimated life expectancy of at least 2 years, in the opinion of the Investigator.
- 14. Have suitable venous access for blood sampling.
- 15. Be willing and able to comply with all study assessments and adhere to the protocol schedule and restrictions.
- 16. A study partner (partner/spouse/carer) consents to the minimum requirements:
 - a. will attend at least one screening visit
 - b. will be available via phone or in person to provide information to the study as required.

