- Haematology, serum chemistry and coagulation tests will be performed (refer to APPENDIX 5). Any new ≥ Grade 3 laboratory abnormality, or change consistent with a possible TEAE (as opposed to disease progression), such as liver function test elevations, electrolyte fluctuation, or hematologic deterioration should be assessed for potential risk to continued dosing. Pre-dose safety laboratory blood samples scheduled for Cycle 1 Day 1 do not need to be repeated if screening blood tests were performed within 4 days prior to study drug administration.
- ¹⁰ ADCS-MCI-ADL24 will be completed by the study partner.
- Standard MRI/PET imaging assessments will be performed during screening and at the EoS visit
- Supply of LorelcoTM or placebo to be provided to the patient for at-home dosing in a Webster pack, with amount provided to last a full cycle.
- Patients to self-administer LorelcoTM or placebo at home, per protocol.
- Adverse events to be monitored throughout the duration of the study.

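### Exclusion criterion 15 is inverted in the synopsis and in Section 7.3: as worded it bars patients who can have the MRI, contradicting the inclusion criteria, the schedule and the MRI endpoint

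*Protocol*

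**What the plan says.** The exclusion list in Section 7.3 opens with the rule "A patient who meets any of the following exclusion criteria will not be eligible for inclusion", and the synopsis has the same rule: "A patient who meets any of the following exclusion criteria will not be eligible for inclusion in the study". In both lists item 15 is "Willing and able to undergo Magnetic Resonance Imaging (MRI". Nothing after it reverses the sense.

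Other parts of the protocol bear on the same matter:

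- Section 7.2, inclusion criterion 15 (item 14 in the synopsis): "Be willing and able to comply with all study assessments and adhere to the protocol schedule and restrictions".
- Section 6.1: "Imaging assessments will be performed at screening, and the 104 week visit or at last study visit if subject discontinues".
- Appendix 1, notes to the schedule: "Standard MRI/PET imaging assessments will be performed during screening and at the EoS visit". The schedule's PET/MRI row carries no restriction to a subset.
- Section 5 lists "volumetric changes in the brain" among the secondary MRI endpoints.
- Section 7.1 goes further for sizing: "Estimated sample sizes are calculated for the two primary outcome measurements: ADAS-Cog and GM atrophy (hippocampal". It asks for 93 per arm (186 in total) on hippocampal volume and says that 233 of the 314 recruits will be picked at random for an Imaging study.
- Section 18.2 states that the sponsor will grant no waivers.

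**The concern.** Eligibility criteria are operative text: sites tick them off and monitors verify them. A requirement for entry has been placed in a list of reasons to refuse entry. Taken at its word, the item removes the very people the MRI endpoint needs, and it conflicts with an inclusion criterion that demands the opposite.

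If sites instead reverse the sense of the line silently, as they probably would, every correctly enrolled scannable participant is on paper an eligibility breach. Nothing in the protocol records how the line was read.

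**Working it through.** The point is decided by the wording, so the main check is one of logic. The imaging target is reproduced first, to show what the criterion bears on.

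**Imaging target.** Inputs from Sections 7.1 and 13.1: a 10.2% hippocampal reduction, a 25% treatment effect, and 6.2 read as the standard deviation. Power of 0.80 is stated there for ADAS-Cog and is assumed for MRI too. Two-sided alpha of 0.05 is also assumed, because it is not stated.

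- Difference: 0.25 × 10.2 = 2.55.
- n per arm = 2 × (1.960 + 0.842)² × (6.2 / 2.55)² ≈ 92.8, rounded up to 93. This matches the plan.
- Attrition: 186 / (1 − 0.20) = 232.5, rounded up to 233. This also matches.

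So the plan needs 186 evaluable scanned patients from 233 recruited to imaging.

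**Literal reading of the criteria.** Take a patient for whom MRI is a study assessment:

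| Patient | Inclusion 15 (able and willing for all assessments) | Exclusion 15 as worded | Result |
|---|---|---|---|
| Willing and able to have MRI | Met | Met, so excluded | Ineligible |
| Unwilling or unable to have MRI | Not met | Not met | Ineligible |

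Both rows end in ineligibility. The number of eligible patients who could supply hippocampal volume is 0, against 186 evaluable as planned. Whichever kind of patient is enrolled, one numbered criterion is breached.

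**Could another line repair it?** Exclusions 1 and 2 are also awkwardly phrased, but each ends with a sentence saying who is to be excluded. Item 15 has no such sentence. No inclusion criterion names MRI.

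**Could it be an artefact of text extraction?** The line is complete, and it carries the same number and wording in two separate lists, so a lost word is not a plausible explanation.

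**The case against.** The strongest reply is that nobody would follow the line literally. It clashes so plainly with inclusion 15, the schedule and the endpoint that a site would read it as intended. That stands, and it is why the practical risk is modest.

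Three stronger readings are tempting, and the protocol does not support them.

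- *Nothing keeps out patients who cannot be scanned.* This is not so. Inclusion 15 covers them in general terms. The closing exclusion (item 24 in the synopsis, unnumbered in Section 7.3) bars those who cannot fully cooperate with what the protocol requires. MRI is also done during screening, so most such patients would be found before dosing. The accurate statement is that the only criterion naming MRI says the opposite of what is meant.
- *The MRI comparison loses power.* If 5% to 10% of the 93 per arm could not be scanned, Φ((2.55/6.2) × √(n/2) − 1.96) gives 80.1% at n = 93, 77.9% at 88 and 76.0% at 84. The arithmetic is right, but the protocol gives no such rate. The calculation also takes the loss on top of the 20% attrition already allowed for, and ignores the 314 − 233 = 81 recruits outside the Imaging study.
- *No patient at all could enter the trial.* This follows only if MRI is an assessment for every participant. Section 7.1 describes imaging as a random subset, while the schedule shows no such limit. The safe claim covers patients for whom MRI is a study assessment.

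It can also be said that this is a clarification of wording, which Section 18.3 treats as administrative when neither safety nor science is affected. For reversing the sense of the line that is fair. Deciding whom the line binds is less clearly administrative, because it affects who may enter.

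**Conclusion.** The point holds as a certain error of wording in an operative rule. Item 15 is inverted in both places and contradicts inclusion 15, the imaging schedule and the volumetric MRI endpoint. Literally applied, it leaves 0 eligible patients among those for whom MRI is a study assessment, and each such enrolment breaches a numbered criterion with no waiver available.

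The likely practical effect is small, because the intent is clear and general criteria already cover patients who cannot be scanned. The conclusion rests on the text alone. It does not depend on the assumed alpha, on reading 6.2 as the standard deviation, or on any rate of MRI contraindication. It should be corrected, but it does not threaten the primary ADAS-Cog analysis.

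**What to change.** In the synopsis and in Section 7.3, either change exclusion 15 to *unwilling or unable to undergo MRI*, or delete it there and place the present wording in the inclusion list.

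In the same amendment, state whether the requirement applies to all participants or only to the 233 in the Imaging study, and align the PET/MRI row of Appendix 1 with that choice.

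The cost is one line in two places, plus the statement of scope. There is a small downside if the requirement is applied to everyone: people who could contribute ADAS-Cog data but cannot be scanned would be kept out of the cognitive study, including some who might never have been chosen for imaging. If it is limited to the Imaging study, the protocol needs to make clear that inclusion 15 does not demand MRI of the others.

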8 INVESTIGATIONAL PRODUCT

8.1 Study Drug Supply

8.1.1 LorelcoTM

LorelcoTM tablets will be supplied by a designated manufacturer/distributor of the Sponsor. The Sponsor will provide the site pharmacy with a sufficient quantity of LorelcoTM for the conduct of the study. The LorelcoTM tablets will be over-encapsulated inside an opaque capsule shell and backfilled with Microcrystalline cellulose. Individual doses of LorelcoTM to be administered in the study will be dispensed by the site pharmacy.

Detailed product information (including storage details) is provided in the Investigator's Brochure.

8.1.2 Placeho

Matching placebo opaque capsules with no active ingredients and a filler of microcrystalline cellulose will be compounded by Oxford Compounding to ensure they are identical in nature. Microcrystalline cellulose was chosen for use in the placebo because it is an inert, insoluble fibre that is not absorbed into the systemic circulation

8.2 Identification and Description of Lorelco(TM)

The probucol used in this study will be commercially available tablets (Lorelco[™] white to slightly yellowish white tablet, diameter 11.1 mm, thickness 4.5 mm) produced by Aventis Pharmaceuticals and wholesaled by Otsuka Pharmaceutical Co., Ltd. for the strength of 250 mg. Oxford Compounding Pharmacy Pty. Ltd. will secure Lorelco[™] 250 mg tablets on behalf of the trial sponsor and will be responsible for over-encapsulation, bottling and dispensing of coded batches to the host sites. Matching placebo capsules with no active ingredients and a filler of microcrystalline cellulose will be compounded by Oxford Compounding to ensure they are identical in nature. Microcrystalline cellulose was chosen for use in the placebo because it is an inert, insoluble fibre that is not absorbed into the systemic circulation.

